c. Selection and Exclusion of Subjects & Randomization procedures

There are two levels of randomization in this study. First, participants were randomly approached on the sidewalk. Social groups arriving at the club together were randomly approached using the portal recruitment methodology (Johnson et al., 2012; Miller et al., 2009, 2013b). The first person to cross an imaginary line on the sidewalk in front of the club was approached to recruit this person and their social group. Nightclubs with at least 200 patrons on a typical weekend night were contacted to seek permission to establish a data collection site outside the club. Clubs held different types of events on different nights, attracting different patrons, depending upon the event being featured. A total of 41 events across 7 nightclubs in the San Francisco area were selected for the data collection from June 2016 through October 2017. These events occurred on Friday and Saturday evenings when the attendance was the greatest. Patrons who were attending the club that evening and were arriving with at least one other person who agreed to participate were considered eligible. Anyone working that evening at the club was not eligible. A total of 352 groups, representing 959 patrons were included in the study. The study was able to recruit 25% of the groups that were stopped and given a description of the study and data collection procedures which included breath tests for estimates of blood alcohol levels and oral fluid samples for detecting drug use and surveys at entrance and exit. Retention for the sample was 88% at exit. Recruitment and data collection occurred outdoors with a data collection site adjacent to the entrance to the club. Participants provided informed consent, and all study procedures were approved by the Pacific Institute for Research Evaluation's Institutional Review Board.

d. Survey and Randomization Procedures

Once patrons agreed to participate in the study, each participant was given a unique number on a wrist band that allowed matching of individuals within a group and entrance/exit data. No names were collected to provide anonymity.

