Computer tablets were handed to each participant to complete the entrance survey. Oral fluid samples for drug analyses and breath tests for determining blood alcohol level were collected during this time by trained research staff. Groups were randomly assigned to either experimental or control after the data for the entire group was collected at baseline. At this point, the research assistant was made aware of the random assignment to either experimental or control condition for the group. Randomization was determined by a randoms number table that determine whether the first group was experimental or control. Given that multiple groups were recruited simultaneously, the supervisor was tracking the assignments of condition and alerting the research assistants as to this assignment. The experimental condition consisted of the Nightlife Safety Plans (NSP) intervention described above. The control condition was given the Fire safety information described above. Given that both the experimental and control group conditions focused on safety in the club, we did not disclose to the participants which safety intervention was under investigation in this study. Once the group finished, they were given an incentive (\$15) and reminded that we would complete a survey when they exited the club with an additional incentive (\$25) offered. As patrons exited the club, they were surveyed again, using the same procedures established at entrance.

e. Measures

Primary Outcomes:

Number of Protective actions to keep the Group Safe: For each individual, five types of actions were assessed related to identifying a potential problem (observing overuse, physical, or sexual aggression) for a friend: There were 5 possible actions to keep their group members safe that were assessed at exit from club (checked in with friends to assess safety during evening, monitored group members alcohol consumption, encouraged pacing drinking, discouraged drug use, encouraged steps to sober up).

Protective action reported for physical aggression incident: Among those who experienced physical aggression, the prevalence of a group member taking action(s) to intervene was reported.

Protective action reported for sexual aggression incident: Among those who experienced sexual aggression, the prevalence of a group member taking action(s) to intervene was reported.

Secondary outcomes

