Protective action reported for sexual aggression incident: Among those who experienced sexual aggression, the percent who reported some protective action by a member of their group was reported.

Legally intoxicated: Percent who were legally intoxicated (BAC.08% or higher). Breath samples provided an estimate of the blood alcohol concentration (BAC) and the MarkV Alcovisor (PAS Systems International, Fredericksburg VA) was used to obtain the breath samples. The estimate of the BAC is presented as measured by this device. Given the short window of time (average of 1 hour 54 minutes, SD=1 hour, 3 minutes) that persons were in the club, only exit BAC is used to reflect drinking and this represents a cumulative total for the evening. Level of intoxication reported which reflects the legal standard of BAC= 0.08% or higher.

Prevalence of recreational drug use: Any use of recreational drugs present in oral fluid tests based upon lab results. Laboratory analyses were conducted using the Quantisal collection device (Immunalysis Corporation, Pomona, CA) to assess the following drug categories: (a)Tetrahydrocannabinol (THC); (b) cocaine, including benzoylecogonine, coaethylene, and norcocaine; (c) amphetamine/e, 4 methylenedioxy-methamphetamine (MDMA), methamphetamine, methylenedioxy-amphetiamen (MDA), and methylenedioxyethylamphetamine (MDEA); (d) opiates/analgesics, including morphine, codeine, oxymorphone, 6-acetylmorphine, hydrocodone, hydropmophone, and oxycodone; (3) methadone; (f) phycyclidine (PCP), and (g) ketamine. Self-report of GHB was also assessed (no lab tests were available for this drug). The prevalence of any drug use at exit from the club was created.

Physical Aggression experienced: Participants were asked at the exit survey whether anyone had intentionally pushed, shoved, or punched you while at the club during the evening.

Sexual aggression experienced: Participants were asked at the exit survey whether anyone had touched you in a sexual way that you did not want or do something else sexual to you that you didn't want them to do.

Leaving club with friends arrived with: The prevalence of the safety action to leave the club with the same friends with whom they arrived.

Females comprised 45.3% of the sample. Ethnicity/race was as follows: 44.2% White, 21.5% Asian, 7.9% African American, 1.7% Pacific Islander, 1.3% Native American, 7.1%

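### Entry breath and oral-fluid results are not named as covariates for the exit alcohol and drug outcomes; if they were left out, precision is lost

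*Combined protocol and SAP*

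**What the plan says.** All references are to the combined protocol and SAP.

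- **Entry collection (III.d).** "Oral fluid samples for drug analyses and breath tests for determining blood alcohol level were collected during this time by trained research staff", that is, while the entrance survey was being completed. Assignment came later: "Groups were randomly assigned to either experimental or control after the data for the entire group was collected at baseline".
- **Exit collection (III.c, III.d).** At exit "they were surveyed again, using the same procedures established at entrance". III.c describes the data collection as "breath tests for estimates of blood alcohol levels and oral fluid samples for detecting drug use and surveys at entrance and exit". Wrist-band numbers link each person's entry and exit data.
- **Outcomes (III.g).** Alcohol: "Percent who were legally intoxicated (BAC.08% or higher"), with the explanation that "only exit BAC is used to reflect drinking and this represents a cumulative total for the evening" because the stay was short (mean 1 hour 54 minutes). Drugs: "The prevalence of any drug use at exit from the club was created".
- **Covariates (III.g).** The outcome models control for background variables, drinking and drug history, and risk level. The background variables are not itemised; the text shows only that some are continuous and some categorical. Risk level comes from entrance survey questions (III.a), not from the samples. Cases with missing data are dropped listwise.
- **Results (IV).** Exit BAC was significantly lower with the intervention. Drug use is described as unaffected, with no difference or interval. The text adds that, in prior research, fewer than 6% of patrons moved from no use at entry to use at exit.

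**The concern.** A baseline measurement of the outcome itself is usually the strongest covariate available, and here it was collected before assignment. The plan's own reasoning implies that it matters. If exit BAC is cumulative, it contains whatever was drunk before entry. If most drug use began before arrival, entry status largely determines exit status. In both cases much of the spread in the exit outcome was fixed before the intervention could act, and it enters the comparison as noise unless the model accounts for it.

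At stake are the width of the intervals and protection against a chance difference between arms in entry intoxication or drug use. This matters most for the drug outcome, where a statement of no effect is made without an interval.

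**Working it through.** The documents give no entry-exit correlation, entry prevalence, intraclass correlation (ICC) or power calculation, so there is no stated figure to reproduce. What follows is illustrative, with assumptions labelled.

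**Sample.** "A total of 352 groups, representing 959 patrons were included in the study" (III.c), with 88% retained at exit. 959 × 0.88 = 844, or 422 per arm if the arms are equal (assumed). 844/352 = 2.40 exit members per group. With an assumed ICC of 0.3 the design effect is 1 + 1.40 × 0.3 = 1.42. It multiplies the variance with and without the entry result alike, so the percentage cuts below do not depend on it.

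**Drug outcome.** Assumed: entry prevalence p = 20-40%; share of entry-positives still positive at exit s = 90-100%; conversion at the 6% ceiling. The 6% may refer to entry-negatives (c = 0.06) or to all patrons (c = 0.06/(1 − p)).

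- Exit prevalence: q = ps + (1 − p)c
- Variance without the entry result: V0 = q(1 − q)(1 − R²), where R² is the share explained by existing covariates
- Variance with it: V1 = ps(1 − s) + (1 − p)c(1 − c)
- Cut = 1 − V1/V0

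| | Low end | High end |
|---|---|---|
| p, s, c | 0.2, 0.9, 0.075 | 0.4, 1.0, 0.06 |
| q | 0.18 + 0.06 = 0.240 | 0.40 + 0.036 = 0.436 |
| V0 at R² = 0 | 0.1824 | 0.2459 |
| V1 | 0.018 + 0.0555 = 0.0735 | 0 + 0.0338 = 0.0338 |
| Cut at R² = 0 | 60% | 86% |
| Cut at R² = 0.3 | 42% | 80% |

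The 95% half-width is 1.96 × √(2V/422). Over the same range, in percentage points, with the values at ICC 0.3 in brackets:

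- no covariates: 5.7-6.7 (6.7-8.0)
- existing covariates explaining 30%: 4.7-5.6 (5.6-6.7)
- with the entry result: 2.5-4.1 (3.0-4.8)

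Preventing every conversion would lower exit prevalence by (1 − p)c, which is 3.6-4.8 points on the entry-negatives reading and 6.0 on the all-patrons reading. Halving conversion would give 1.8-3.0 points, against an adjusted half-width of 2.5-4.1 before clustering. So adjustment helps, but low conversion still limits what can be detected.

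**Chance imbalance.** One standard deviation of the between-arm difference in entry prevalence is √(2p(1 − p)/422) = 2.8-3.4 points (3.3-4.0 at ICC 0.3).

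**Alcohol outcome.** Assumed: existing covariates correlate 0.3-0.5 with exit BAC (Rx) and with entry BAC (Re); entry-exit correlation ρ = 0.4-0.8; 20-50% at or above .08%. With partial correlation r = (ρ − RxRe)/√((1 − Rx²)(1 − Re²)), the cut for continuous BAC is r². For the threshold outcome under a latent normal, T = Rx² + (1 − Rx²)r², k = φ(t)²/(q(1 − q)), where q is now the share at or above .08% and t the matching normal cut-point. The cut is 1 − (1 − kT)/(1 − kRx²).

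Example: ρ = 0.6, Rx = Re = 0.3, q = 0.3. Then r = 0.51/0.91 = 0.560, T = 0.376, k = 0.576, and the cut is 1 − 0.784/0.948 = 17%.

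| ρ | .08% outcome | Continuous BAC |
|---|---|---|
| 0.4 | 2-7% | 4-12% |
| 0.6 | 9-19% | 22-31% |
| 0.8 | 23-38% | 54-62% |

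**Bias.** A simulation of 352 randomised groups (1,500 replicates; assumed ρ 0.7, ICC 0.3, true effect −0.20 SD) gave bias of about zero with and without the entry value. This held with full follow-up and with about 12% exit loss related to entry level equally in both arms. When loss depended on entry level in one arm only, the unadjusted estimate drifted by −0.05 SD; with opposite dependence in the two arms, by −0.09 SD. Adjustment removed the drift.

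**The case against.** The strongest reply is that omission is not shown. The sentence about using only exit BAC defines an outcome; it does not list covariates. A reader might infer from it that the entry readings were ignored in the models, but the unlisted background variables could include them. This stands: what is certain is under-specification.

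It also stands that the outcomes are secondary, that the reported BAC effect is already significant, that drug history and risk level may recover part of the loss, and that every size above rests on assumed inputs. Section IV is an overview that gives no estimate for any outcome, and it already says that few patrons convert. Any new model would be post hoc. The difference between the listed .08% outcome and the reported lower BAC is a separate reporting matter and adds no weight to the covariate point.

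What does not stand is the idea that listing the covariates would be enough whatever the list shows. The entry results are pre-assignment, held and linkable. A short stay and a cumulative reading can justify exit BAC as the outcome; they give no reason to leave entry BAC out as a covariate.

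**Conclusion.** The point holds as a minor one. The entry results are eligible covariates that the plan does not name. If they were left out, precision and protection against chance imbalance were lost: possibly a large share of the variance for drug use, and anything from negligible to moderate for the .08% outcome, depending on correlations that the documents do not give.

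Two stronger readings are tempting and are not supported. The first is that the exit-only comparisons are biased. Leaving out a baseline covariate does not bias a randomised comparison. That assurance needs sound allocation and exit loss that does not depend on entry level differently by arm. The documents settle neither condition: retention is given only overall, and III.d describes the random number table as fixing the first group's condition, with a supervisor tracking later assignments. Not knowing is not evidence of bias. The second is that the drug finding conceals a real effect. Low conversion would limit that comparison even after adjustment.

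**What to change.** 1. In III.g, list the background variables and state whether entry BAC and the entry oral-fluid result were in the outcome models. If they were, this sentence settles the covariate point.
2. If they were not, add entry BAC (continuous) to the exit alcohol models and the entry oral-fluid result to the exit drug model. Keep the listed outcomes and label the analysis post hoc. For the binary outcomes report a standardised risk difference, because adding a strong covariate changes what an odds ratio means. Report the number of missing entry results, and entry balance and exit retention by arm.
3. In IV, replace the statement that drug use was unaffected with the estimated difference and its confidence interval.
4. As a separate reporting correction, give the listed .08% result and label mean exit BAC as additional.

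The cost is a small re-run on held data, some rewording and post hoc status. Listwise deletion would drop people without an entry result; for the .08% outcome at an entry-exit correlation of 0.4, a missing share above the 2-7% variance cut would cancel the gain. If nearly all entry-positives stay positive, a logistic coefficient for the entry result may not be estimable, and a risk-difference model would be needed.

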AA022331-NCT3652688

Updated 1-9-25

Study Protocol and Statistical Analyses for

Group-based Intervention for Alcohol, Drugs and Aggression Among Club Patrons AA022331

Principal Investigator:

[name]., Prevention Research Center, PIRE, Berkeley, CA

Co-Investigators:

[name]., Prevention Research Center, PIRE, Berkeley, CA

[name]., Prevention Research Center, PIRE, Berkeley, CA

[name]., Prevention Research Center, PIRE, Berkeley, CA

[name], Ph. D., Klein Buendel, Golden, CO.

Project Coordinator:

[name], B.S., Prevention Research Center, PIRE, Berkeley, CA

I Background information

Our prior research indicated that most (91.6%) of club patrons arrive in groups (Miller, et al., 2015). Considerable evidence indicates that peers can influence drinking and drug use (Dumas et al., 2014; O'Grady et al., 2011; Phua, 2011). The peer group can engage in preventive or protective behaviors for group members (Boekeloo &Griffin, 2009; Boekeloo et al., 2009) and prior research indicates a willingness for club patrons to look out for each other when in the club environment (Byrnes et al., 2016).

II. Purpose of Study

Our primary purpose was to engage groups of young adults who are planning an evening of partying at nightclubs and to determine whether the social group that arrived together would protect each other from harms related to drinking and drug use and partying. The intervention was designed to provide skills to identify early signs of alcohol/drug related problems as well as threats to personal safety from aggression. The intervention provided skills for individuals to intervene with each other to avoid unwanted outcomes like overuse of alcohol/drugs, experiences of aggression (physical/sexual). The primary outcome was to increase these protective actions within the group. Secondary outcomes included decreasing actual alcohol/drug use and experiences of aggression.

III. Study Design

a. Description of intervention

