Exposure to the intervention, NSP, significantly increased the number of safety actions taken within the group to protect others in their group from the unintended consequences from behaviors and experiences in the club that evening related to alcohol use and drug use (Byrnes, Miller, et al., 2019a). The study found that group cohesion related to fewer safety strategies being used and that group cohesion was unrelated to AOD use (Byrnes, Miller, et al., 2019b). This suggests that more risk taking behavior may occur when groups are familiar and comfortable with each other, possibly lowering their sense of risks. The relatively low rates of experiencing physical and sexual aggression impacted the power of the intervention to assess protective actions related to physical or sexual incidents that occurred in the evening. Although the main focus of the intervention was on taking actions to reduce harms, there was also an impact on a secondary outcome related to alcohol use. For participants exposed to NSP, there was a significantly lower BAC at exit. Prevalence of recreational drug use was not impacted by the intervention but prior research (Miller et al., 2013b) indicates that few club patrons (<6%) convert from no drug use at entry to drug use at exit, indicating that recreational drug use has already been initiated prior to coming to the club. The intervention did not significantly alter the rates of physical or sexual aggression while at the club. However, aggression experiences are less under the control of the participants as persons outside the group can be the offender in these incidents. Thus, the group can respond and de-escalate the impact of the aggression but may not be effective at keeping aggressive incidents from happening. Finally, participants exposed to the intervention were significantly more likely to leave as a group and "stick together." Given that the intervention was focused on promoting looking after each other for the evening,

this was an important safety impact. There are anecdotal reports of individuals leaving the club with someone they just met or being assaulted while traveling home by themselves. However, data on the prevalence of this type of experience is not available from prior studies or this study.

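### Exit BAC is a concentration at departure, not a cumulative total, so a lower exit BAC does not by itself show that less alcohol was drunk

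*Combined protocol and SAP*

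**What the plan says.** Section II sets the aim: "Secondary outcomes included decreasing actual alcohol/drug use and experiences of aggression".

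Section III.g, under the legal intoxication outcome, explains how alcohol is measured. The breath device gives an estimate of blood alcohol concentration, and the outcome is a cut-off on that reading: "Level of intoxication reported which reflects the legal standard of BAC= 0.08% or higher". The reason for using the exit reading alone is "Given the short window of time (average of 1 hour 54 minutes, SD=1 hour, 3 minutes) that persons were in the club", from which the section concludes that "only exit BAC is used to reflect drinking and this represents a cumulative total for the evening".

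An entry reading also exists. Section III.d says of the entrance survey period: "Oral fluid samples for drug analyses and breath tests for determining blood alcohol level were collected during this time by trained research staff". Groups were assigned only after the whole group's baseline data were in. The outcome models in Section III.g adjust for background characteristics, past drinking and drug use, and risk level. They name neither entry BAC nor any measure of elapsed time.

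Section IV reports a significantly lower exit BAC with the Nightlife Safety Plans intervention (NSP) and presents it as an effect on a secondary outcome connected with alcohol use. It gives no size or SD. It also reports that "participants exposed to the intervention were significantly more likely to leave as a group".

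**The concern.** Section III.g describes one quantity in two ways that cannot both be right. A concentration read at one moment is not a running total, because alcohol is eliminated while the evening goes on. Two patrons who drank the same amount can leave with different readings if one started earlier, drank over a longer time or waited longer before the test.

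This matters because Section II's aim concerns alcohol use. Some of the actions counted in the primary index in Section III.e are "encouraged pacing drinking, discouraged drug use, encouraged steps to sober up". Drinking the same amount over a longer period, or allowing more time to sober up before leaving, could lower the exit reading with no change in intake. So could a different length of stay. If exit BAC is taken as a total, any lower reading is counted as less drinking, and the trial's conclusion on alcohol use goes further than its measure.

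**Working it through.** The document states no effect size, SD or design figure for BAC, so there is no figure to reproduce. The check asks whether the short-stay argument makes elimination negligible.

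**Inputs from Section III.g.** Mean stay 1 h 54 min = 1.90 h; SD 1 h 3 min = 1.05 h, both pooled over arms; cut-off 0.08%.

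**Assumption, not in the document.** Elimination at a constant rate k of 0.010 to 0.020 % per hour while the reading is above zero.

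1. Loss over the mean stay = k × 1.90 h. This gives 0.010 × 1.90 = 0.019 % to 0.020 × 1.90 = 0.038 %. As a share of the cut-off: 0.019/0.08 = 24% to 0.038/0.08 = 48%.

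2. Loss per SD of stay = k × 1.05 h, or 0.0105 to 0.021 %.

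3. Same intake, different elapsed time. Take an illustrative intake equivalent to 0.100 %, fully absorbed, with exit BAC = 0.100 − k × t. The times are the mean stay and one SD either side (0.85, 1.90 and 2.95 h).

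| k (%/h) | 0.85 h | 1.90 h | 2.95 h |
|---|---|---|---|
| 0.010 | 0.0915 | 0.0810 | 0.0705 |
| 0.015 | 0.0873 | 0.0715 | 0.0558 |
| 0.020 | 0.0830 | 0.0620 | 0.0410 |

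At every rate in the range, one intake falls on both sides of 0.08% depending only on elapsed time. Alcohol drunk before arrival has had longer still to clear. In this formula, pacing and sobering up lower the reading at equal intake only so far as they lengthen the time between drinking and the test.

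4. What an arm difference in elapsed time would do. A difference of 15 minutes (illustrative; none is reported) gives 0.25 × 0.010 to 0.25 × 0.020 = 0.0025 to 0.005 % at equal intake.

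5. Whether a comparison of stay by arm would be informative. Detectable difference = 63 min × (1.960 + 0.842) × √(2/n), assuming two-sided alpha 0.05, 80% power and equal arms. With 88% exit retention (Section III.c):
   - if members of a group have identical stays, n = 0.88 × 352/2 ≈ 155 per arm, giving about 20 min;
   - if stays are independent within groups, n = 0.88 × 959/2 ≈ 422 per arm, giving about 12 min.

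   Clustering by event is ignored here.

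**The case against.** The best defence is that the endpoint is a state at exit. Section III.e defines it as being legally intoxicated, and BAC at departure is the right quantity for that. Under randomization, any effect through pacing, sobering up or timing is part of the intervention's effect on exit intoxication and not a bias. All of this stands. Section IV's result sentence also already names BAC at exit, so part of the claim is properly worded.

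The arithmetic shows no difference between arms. The loss over the mean stay occurs in both arms and cancels unless elapsed time differs, and the SD of stay is variation between people that randomization spreads over the arms. The calculations hold intake fixed, although a longer stay also allows more drinking. Without a reported BAC effect, nobody can say whether 0.0025 to 0.005 % is large against it. This also stands: the figures show only that elimination is not negligible.

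A reader might infer from the finding on leaving as a group that NSP patrons waited for friends, stayed longer and so had lower readings. The document does not support this. The item in Section III.e asks with whom patrons left, not when, and leaving together could equally mean leaving earlier.

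Finally, Section III.g says descriptive analyses were done by arm without listing every variable, and the results are cited to a publication not examined here. It can be said only that this document does not report stay by arm.

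None of this rescues the description of exit BAC as a cumulative total, or the use of that description to link the result to alcohol use.

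**Conclusion.** The point holds for what exit BAC is said to measure. It is a concentration at departure, and the short stay does not turn it into a total: at the assumed 0.010 to 0.020 % per hour, the mean stay removes 0.019 to 0.038 % from a patron whose reading stays above zero, a quarter to a half of the cut-off. The qualitative conclusion needs only the fact that alcohol is eliminated over time; the size rests on the assumed rate.

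The randomized comparison of intoxication at exit is not invalidated. What is unsupported is the step from a lower exit reading to a reduction in actual alcohol use. Nor does the document show that intake was unchanged; less drinking remains a plausible explanation. The stronger reading, that NSP altered departure time and so produced the BAC result, is not shown, and its direction would be open.

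**What to change.** - In Section III.g, replace the statement that exit BAC is a cumulative total with one that it is the concentration at departure.
- Report time between the entrance and exit tests by arm, from the data behind the 1 h 54 min figure. Keep this descriptive. Elapsed time arises after assignment and should not enter the outcome model as a covariate.
- Add a sensitivity model of exit BAC, and of BAC at or above 0.08%, adjusted for the entry BAC taken before assignment. This accounts for drinking before entry as a baseline covariate; it does not turn the outcome into a measure of intake.
- In Section IV, state the result as lower BAC at exit, not as reduced alcohol use.

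An intake estimate of the form exit BAC minus entry BAC plus rate times hours is not recommended. A patron who reads zero at both tests over 1.90 h would be credited with 0.019 to 0.038 % of alcohol never drunk, and a longer stay would add more.

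The cost is two wording changes, one descriptive row and one sensitivity analysis for each form of the outcome, all on data already held. The small downside is a narrower alcohol claim.
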